#### Abnormal Test Findings

The criteria for determining whether an abnormal objective test finding should be considered clinically significant and therefore reported as an AE are as follows:

- Test result is associated with accompanying symptoms, and/or
- Test result requires additional diagnostic testing or medical/surgical intervention, and/or
- Test result leads to a change in study dosing (outside of protocol-stipulated dose adjustments) or discontinuation from the study, significant additional concomitantdrug treatment or other therapy, and/or
- Test result is considered to be an AE by the investigator or sponsor.

Merely repeating an abnormal test, in the absence of any of the above conditions, does not constitute an AE. Any abnormal test result that is determined to be an error does not require reporting as an AE.

#### Serious Adverse Events

An SAE is any untoward medical occurrence at any dose that:

- Results in death;
- Is life-threatening (immediate risk of death);
- Requires inpatient hospitalization or prolongation of existing hospitalization;
- Results in persistent or significant disability/incapacity (substantial disruption of the ability to conduct normal life functions);
- Results in congenital anomaly/birth defect.
- Other serious (important medical event)

Each AE is to be assessed to determine if it meets the criteria for SAEs.

Progression of the malignancy under study is an AE but **should not** be reported as an SAE unless the outcome is fatal or meets other SAE criteria AND occurs within the reporting period defined in Section 13.3. In these situations, every effort should be made to report the signs and symptoms of progression as the event(s) meeting criteria as an SAE unless otherwise not feasible.

Medical and scientific judgment is exercised in determining whether an event is an important medical event. An important medical event may not be immediately life-threatening and/or result in death or hospitalization. However, if it is determined that the event may jeopardize the patient or may require intervention to prevent one of the other AE outcomes, the important medical event should be reported as serious.

Examples of such events are intensive treatment in an emergency room or at home for allergic bronchospasm; blood dyscrasias or convulsions that do not result in hospitalization; or development of drug dependency or drug abuse.

## **SAE Reporting Requirements**

If an SAE occurs, the sponsor is to be notified within 24 hours of the site investigator or other site personnel become aware of the event, using the sponsor's forms and routes pre-specified in the protocol procedures manual.

In particular, if the SAE is fatal or life-threatening and meets other reporting requirements, notification to the sponsor must be made immediately, irrespective of the extent of AE information. This timeframe also applies to additional new information (follow-up) on previously forwarded SAE reports as well as to the initial and follow-up reporting of exposure during pregnancy and exposure via breastfeeding cases.

For all SAEs, the investigator is obligated to pursue and provide information to the sponsor in accordance with the timeframes for reporting specified above. In addition, an investigator may be requested by the sponsor to obtain specific additional follow-up information in an expedited fashion. In general, this will include a description of the adverse event in sufficient detail to allow for a complete medical assessment of the case and independent determination of possible causality.

Information on other possible causes of the event, such as concomitant medication and illnesses must be provided. In the case of a patient death, a summary of available autopsy findings must be submitted as soon as possible to the sponsor or its designated representative.

Confidential

## Protocol-Specified Serious Adverse Events

The following expected SAEs will be reported by the investigator as described in previous sections, and will be handled as SAEs in the safety database but will not be reported individually in an expedited manner to regulatory authorities because they are anticipated to occur in the study population:

- Infections or complications from central lines or feeding tubes.
- AEs related to loco-regional or metastatic extension of the disease including central nervous system involvement of disease.

#### Hospitalization

Adverse events associated with hospitalization or prolongations of hospitalization are considered serious. Any initial admission (even if less than 24 hours) to a healthcare facility meets these criteria. Admission also includes transfer within the hospital to an acute/intensive care unit (e.g., from the psychiatric wing to a medical floor, medical floor to a coronary care unit, neurological floor to a tuberculosis unit):

Hospitalization does not include the following:

- Rehabilitation facilities;
- Hospice facilities;
- Respite care (e.g., caregiver relief);
- Skilled nursing facilities;
- Nursing homes;
- Emergency room visit that does not result in admission;
- Same day surgeries (as outpatient/same day/ambulatory procedures).

Hospitalization or prolongation of hospitalization in the absence of a precipitating, clinical adverse event is not in itself a serious adverse event. Examples include:

- Admission for treatment of a preexisting condition not associated with the development of a new adverse event or with a worsening of the preexisting condition (e.g., for work-up of persistent pre-treatment lab abnormality);
- Social admission (e.g., patient has no place to sleep);
- Administrative admission (e.g., for yearly physical exam);
- Protocol-specified admission during a study (e.g., for a procedure required by the study protocol);
- Optional admission not associated with a precipitating clinical adverse event (e.g., for elective cosmetic surgery);
- Hospitalization for observation without a medical AE;
- Pre-planned treatments or surgical procedures should be noted in the baseline documentation for the entire protocol and/or for the individual patient;
- Admission exclusively for the administration of blood products.

Diagnostic and therapeutic non-invasive and invasive procedures, such as surgery, should not be reported as AEs. However, the medical condition for which the procedure was performed should be reported if it meets the definition of an AE. For example, an acute appendicitis that begins during the AE reporting period should be reported as the AE, and the resulting appendectomy should be recorded as treatment of the AE.

#### Severity Assessment

If required on the adverse event case report forms, the investigator will use the definitions of Severity in accordance with CTCAE Version 5.0 to describe the maximum intensity of the adverse event. If the event is serious, the CTCAE grade reported in the adverse event CRF must be consistent with the description of CTCAE grade included in the narrative section of the serious adverse event report. Event-specific CTCAE grading must be used if available; otherwise the general grading system below should be applied.

# Table 10: CTCAE v5.0 general grading system for adverse events. See the CTCAE v5.0 for
AE specific grading.

Grade	Clinical Description of Severity
0	No change from normal or reference range (This grade is not included in Version
	4.0 document but may be used in certain circumstances.)
1	Mild; asymptomatic or mild symptoms; clinical or diagnostic observations only; intervention not indicated.
2	Moderate; minimal, local or noninvasive intervention indicated; limiting age-appropriate instrumental Activities of Daily Living.*
3	Severe or medically significant but not immediately life-threatening; hospitalization or prolongation of hospitalization indicated; disabling; limiting self-care Activities of Daily Living.**
4	Life-threatening consequences; urgent intervention indicated.
5	Death related to AE.

\*Instrumental ADL refer to preparing meals, shopping for groceries or clothes, using the telephone, managing money, etc.

\*\*Self-care ADL refer to bathing, dressing and undressing, feeding self, using the toilet, taking medications, and not bedridden.

Note the distinction between severity and the seriousness of an adverse event. A severe event is not necessarily a serious event. For example, a headache may be severe (interferes significantly with patient's usual function) but would not be classified as serious unless it met one of the criteria for serious adverse events, listed above.

#### Causality Assessment

The investigator's assessment of causality must be provided for all AEs (serious and non-serious); the investigator must record the causal relationship in the CRF, as appropriate, and report such an assessment in accordance with the serious adverse reporting requirements, if applicable. An investigator's causality assessment is the determination of whether there exists a reasonable possibility that the investigational product caused or contributed to an AE. If the investigator does

not know whether or not investigational product caused the event, then the event will be handled as "related to investigational product" for IND or other regulatory authority reporting purposes, as defined by the sponsor (see Section on Reporting Requirements). If the investigator's causality assessment is "unknown but not related to investigational product," this should be clearly documented on study records and the SAE report.

In addition, if the investigator determines an SAE is associated with study procedures, the investigator must record this causal relationship in the source documents and CRF, as appropriate, and report such an assessment in accordance with the serious adverse event reporting requirements, if applicable.

The Investigator will assign attribution of the possible association of the event with use of the investigational drug, and this information will be entered onto CRFs as either related or unrelated to the investigational agent. All AEs judged to be possibly, probably or definitely related to the investigational agent should be assigned the "related" designation. The Investigator will also assign attribution for study procedures.

## 13.11.1Suspected

A suspected adverse reaction is defined as any adverse event for which there is a reasonable possibility that the drug caused the adverse event. For the purposes of IND safety reporting and reporting to other regulatory authorities, "reasonable possibility" indicates that there is evidence to suggest a causal relationship between the drug and the adverse event. A suspected adverse reaction implies a lesser degree of certainty about causality than an adverse reaction.

## 13.11.2Unexpected

An AE or suspected adverse reaction is considered *unexpected* if it is not listed in the IB or package insert(s) or is not listed at the specificity or severity that has been observed, or, if an IB is not required or available, is not consistent with the risk information described in the general investigational plan or elsewhere in the current application.

"Unexpected," as used in this definition, also refers to adverse events or suspected adverse reactions that are mentioned in the investigator brochure as occurring with a class of drugs or as anticipated from the pharmacological properties of the drug but are not specifically mentioned as occurring with the particular drug under investigation.

Except as specified in Section 13.10, AEs that would be anticipated to occur as part of the disease process are considered *unexpected* for the purposes of regulatory authority reporting because they would not be listed in the IB. For example, a certain number of non-acute deaths in a cancer trial would be anticipated as an outcome of the underlying disease, but such deaths would generally not be listed as a suspected adverse reaction in the IB.

Some AEs are listed in the IB as occurring with the same class of drugs, or as anticipated from the pharmacological properties of the drug, even though they have not been observed with the drug under investigation. Such events would be considered *unexpected* until they have been observed with the drug under investigation. For example, although angioedema is anticipated to occur in some patients exposed to drugs in the ACE inhibitor class and angioedema would be described in the IB as a class effect, the first case of angioedema observed with the drug under investigation should be considered *unexpected* for reporting purposes.

#### **Exposure During Pregnancy**

The definition of exposure during pregnancy (also referred to as in utero) is met if:

- A female becomes, or is found to be, pregnant either while receiving or being exposed to (e.g., due to treatment or environmental exposure) or after discontinuing or having been directly exposed to the investigational product;
- A male has been exposed to the investigational product prior to or around the time of conception and/or is exposed during his partner's pregnancy.

If any study patient or study patient's partner becomes or is found to be pregnant during the study patient's treatment with the investigational product, the investigator must submit this information to the sponsor. In addition, the investigator must submit information regarding environmental exposure to the sponsor. This must be done irrespective of whether an AE has occurred and within 24 hours of awareness of the exposure. The information submitted should include the anticipated date of delivery. The investigator will follow the pregnancy until completion or until pregnancy termination. Further follow-up of birth outcomes will be handled on a case-by-case basis.

#### Withdrawal Due to an AE

Withdrawal due to AE should be distinguished from withdrawal due to insufficient response, according to the definition of adverse event noted earlier and recorded on the appropriate adverse event CRF page.

When a patient withdraws due to an SAE, the SAE must be reported in accordance with the reporting requirements defined below.

#### Follow-up of AEs

All adverse events will be followed with appropriate medical management until resolved. Patients removed from study for unacceptable adverse events will be followed until resolution or stabilization of the adverse event. For selected adverse events for which administration of the investigational drug was stopped, a re-challenge of the subject with the investigational drug may be conducted if considered both safe and ethical by the Investigator.

# 14 DATA ANALYSIS/STATISTICAL METHODS

As the primary purpose of this study is to evaluate and characterize the safety profile of single agent VK-2019, and evaluate preliminary efficacy, no confirmatory inferential analyses are planned. Descriptive statistics (such as means, medians, standard deviations and ranges for continuous data and percentages for categorical data) will be used to summarize patient characteristics, treatment administration/compliance, efficacy, and safety, pharmacodynamic and pharmacokinetic parameters. Data will also be displayed graphically where appropriate.

## Phase 1 Endpoints

14.1.1 Primary Endpoints

• The frequency, severity, and duration of AEs and DLTs, AEs leading to discontinuation. and AEs leading to death.

## 14.1.2 Secondary Endpoints

- The rate and severity of treatment emergent AEs at the MTD and BCAD.
- Single dose and steady state plasma pharmacokinetic parameters of VK-2019.
- Incidence of safety laboratory assessment abnormalities
- Incidence of abnormalities in vital signs or other clinical safety assessments
- ORR, DOR, and Disease control rate (DCR) per RECIST v1.1
- Rate of partial or complete plasma EBV-DNA antiviral response during treatment (assessed as  $3x\log^{10}$  reduction or a drop below the lower limit of detection of the assay [LLOD], respectively).

## 14.1.3 Exploratory Endpoints

• Exploratory analysis of relationships among PK, PD and clinical activity in order to preliminarily define BCAD.

# Phase 2a Endpoints

## 14.2.1 Primary Endpoints

• The durable ORR rate as well as ORR, DOR, DCR-6, DCR-12, PFS, rate of survival, and OS per RECIST v1.1.

## 14.2.2 Secondary Endpoints

- The rate and severity of treatment emergent AEs at the MTD, BCAD, and RP2D.
- Rate of partial or complete plasma EBV-DNA antiviral response during treatment (assessed as  $3x\log^{10}$  reduction or a drop below the lower limit of detection of the assay [LLOD], respectively).
- Plasma PK parameters of VK-2019.

# 14.2.3 Exploratory Endpoints

• Exploratory PD assay for EBER in situ hybridization levels in baseline and on treatment tumor biopsies in a limited number of patients at RP2D.

## Sample Size Determination

The number of patients in the dose escalation phase is estimated to be 30 patients (assuming six patients will be dosed in each of five cohorts). The number of patients in the Phase 1 Dose Expansion and Phase 2a Dose Expansion is based on a Simon 2-stage design as described below. The approximate sample size in the Phase 1 Dose Expansion is estimated to be 20 patients (assuming 10 additional patients in each of two expanded dose levels). During the Phase 2a portion of the trial, the approximate sample size in the Phase 2a Dose Expansions is estimated to be 18 (assuming 9 patients in each of two expansion cohorts). In total, it is estimated that up to approximately 68 patients will be dosed in this trial.

The number of patients for the Phase 1 and 2a expansions is based upon a Simon Two-Stage design at BCAD and MTD, respectively. The null hypothesis that the true response rate is 0.1 will be tested against a one-sided alternative. In the first stage (i.e., a Phase 1 Dose Expansion cohort), a total of 16 patients will be accrued. If there is one or fewer responses in these 16 patients, accrual to this cohort will be stopped. Otherwise, 9 additional patients will be accrued (i.e., a Phase 2a Dose Expansion cohort) for a total of 25. The null hypothesis will be rejected if five or more responses are observed in 25 patients. This design yields a 1-sided type I error rate of 10% and power of 90% when the true response rate is 30%. This design yields a probability of 0.51 for a cohort stopping early if the true response rate for that cohort is 10%. The sample size in the dose escalation phase is not based on statistical considerations, but rather depends on the number of observed toxicities; up to 6 subjects are expected to be treated after the accelerated titration design has ended at each conventional escalation cohort dose prior to the expansion cohort at MTD.

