### Phase 1 Dose Expansion

During dose escalation, one or more cohorts may be selected for expansion, enrolling up to 16 patients (inclusive of the patients already enrolled at the same dose during escalation) at any dose level that is assessed to either be the MTD or have sufficient activity to meet criteria as a BCAD. See Section 6.7 for details on initiating a Phase 1 Dose Expansion.

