#### **Definition of the MTD**

The MTD is defined as the highest dose level of VK-2019 at which fewer than two DLTs are observed in six evaluable dose escalation patients at that dose level.

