#### **Definition of a BCAD**

A BCAD is defined as any dose level that appears to have preliminary clinical or biological activity based upon the following criteria:

- There are no safety concerns in that cohort based upon the SRC's analysis of safety data.
- The following criteria for either clinical or biological activity:

Clinical:

• At least one dose escalation patient has experienced an objective response per RECIST v1.1 (i.e., a PR or CR) at that dose level.

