#### Initiation of Phase 1 Expansion Cohorts

The SRC may elect to initiate a Phase 1 Dose Expansion Cohort and enroll additional patients at any dose level that:

- Meets the definition of the MTD.
- Meets the definition of a BCAD.

The total number of patients enrolled at any one dose level during Phase 1 (dose escalation and expansion) will not exceed 16 patients.

Based upon the above criteria, the SRC may elect to explore multiple dose levels as Phase 1 Expansion Cohorts (either staggered or concurrently).

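### The stated 0.51 early-stop probability assumes a first 16 not selected on response; for an expansion opened solely by an escalation patient's response, it is 0.21 to 0.26 if every response counts

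*Protocol*

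**What the plan says.** Protocol Sample Size Determination (Section 14), the synopsis and SAP Section 5 describe the same two-stage rule. A response rate of 10% is tested one-sided. Accrual stops at one or fewer responses in 16; "Otherwise, 9 additional patients will be accrued", and the null is rejected at five or more responses in 25. The stated properties are type I error 10%, power 90% at a 30% rate, and, for futility, "This design yields a probability of 0.51 for a cohort stopping early if the true response rate for that cohort is 10" percent. The expansions are "based upon a Simon Two-Stage design at BCAD and MTD, respectively".

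Three other places determine who the first 16 are:

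- Phase 1 Dose Expansion (Section 4; SAP 2.1.2) makes the 16 "inclusive of the patients already enrolled at the same dose during escalation". The sizing agrees: six per escalation cohort, then "assuming 10 additional patients in each of two expanded dose levels".
- Definition of a BCAD, clinical criterion: "At least one dose escalation patient has experienced an objective response per RECIST v1.1" at that dose level.
- Initiation of Phase 1 Expansion Cohorts lets the Safety Review Committee expand a dose level that is the MTD or that "Meets the definition of a BCAD".

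None of the three statements of the 0.51 mentions that a cohort may have been opened because of a response that is then counted in stage 1.

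**The concern.** Stage 1 needs two responses to continue. If the cohort exists only because an escalation patient responded, and that patient is one of the 16, it starts with at least one of them. The 0.51 treats all 16 as a fresh binomial sample, which they no longer are.

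Stage 1 is the only response-based futility check between the Phase 1 expansion and nine further patients. A committee that relies on 0.51 for such a cohort would believe the check stops an ineffective dose about twice as often as it does. The pooled response rate would also contain the response that opened the cohort, and would read high.

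**Working it through.** **Inputs.** p = 0.10 (null) or 0.30 (alternative); 16 + 9 patients; stop at ≤1/16; reach at ≥5/25 (Sample Size Determination). k is the number of escalation patients carried into the 16: 1 in an accelerated titration cohort and 3 to 6 in a rolling six cohort (Section 6.2.1); the planned ten additional patients imply k = 6. Every response counts, as in Sample Size Determination and Interim Analysis. Responses are assumed independent with a common rate, and all patients assessable.

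**Step 1: the plan's own figures.** P(≤1 of 16) at 10% = 0.9^16 + 16 × 0.1 × 0.9^15 = 0.1853 + 0.3294 = 0.515. Exact enumeration of both stages gives type I error 0.095 and power 0.903. All agree with the stated 0.51, 10% and 90%.

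**Step 2: condition on opening.** The cohort opens if at least one of the k responds, with probability 1 − (1 − p)^k. It then stops only if exactly one of the k responds and none of the other 16 − k does:

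P(stop | opened) = k·p·(1 − p)^15 / [1 − (1 − p)^k].

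For k = 6 at 10%: 6 × 0.1 × 0.2059 / (1 − 0.5314) = 0.1235 / 0.4686 = 0.264.

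P(reach | opened) sums, over x ≥ 1 responses in the k and y in the other 16 − k with x + y ≥ 2, the binomial probabilities times P(at least 5 − x − y of 9), divided by the same denominator. Expected response rate in the first 16 is [k·p/(1 − (1 − p)^k) + (16 − k)·p]/16.

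| | Unselected | k = 1 | k = 3 | k = 6 |
|---|---|---|---|---|
| P(open) at 10% | – | 0.100 | 0.271 | 0.469 |
| Early stop given opening, 10% | 0.515 | 0.206 | 0.228 | 0.264 |
| Reach 5/25 given opening, 10% | 0.095 | 0.213 | 0.193 | 0.167 |
| Expected response rate in first 16, true 10% | 10% | 15.6% | 15.0% | 14.3% |
| Reach 5/25 given opening, 30% | 0.903 | 0.956 | 0.946 | 0.932 |

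Simulation of early stopping gave 0.204, 0.226 and 0.262 for k = 1, 3 and 6.

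**Step 3: the same events per dose level tried.** For a dose that can open only this way:

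| | k = 1 | k = 3 | k = 6 |
|---|---|---|---|
| Opens and reaches 5/25, 10% | 0.021 | 0.052 | 0.078 |
| Never reaches the nine extra patients, 10% | 0.92 | 0.79 | 0.65 |
| Opens and reaches 5/25, 30% | 0.29 | 0.62 | 0.82 |

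The middle row is P(not opened) + P(opened and stopped); for k = 6, 0.531 + 0.124 = 0.655.

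**Step 4: sensitivity to the response definition.** The documents differ. Sample Size Determination counts responses without qualification, and Interim Analysis does not require confirmation. Initiation of Phase 2a Expansion Cohorts, Section 4 and SAP 2.1.3 require two responses with at least one confirmed. The efficacy definition in 14.5.2 and SAP 7.13 requires confirmation for every responder. The Phase 2a hypothesis concerns durable responses. The share of responses that are confirmed, s, is not given, so 60 to 90% is assumed, with k = 6 and opening on any response.

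- Two responses, at least one confirmed: early stop given opening is 0.16 to 0.34, always 50 to 60% of the unselected value under the same rule. At s = 80%: 0.20 against 0.40 if 10% is the confirmed rate, and 0.28 against 0.53 if 10% is the any-response rate.
- Two confirmed responses, any-response rate 10%, c = 0.1s. The unselected value is U = (1 − c)^16 + 16c(1 − c)^15. Given opening, it is [U − 0.9^6 × P(≤1 confirmed of 10)] / (1 − 0.9^6). At s = 80 / 70 / 60% this gives 0.42 / 0.51 / 0.60, against unselected 0.63 / 0.69 / 0.75.

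**Step 5: response-evaluable patients.** Inclusion criterion 7 requires measurable disease only for the expansions, while the interim counts 16 dosed. If 1 / 2 / 3 of an unselected 16 (assumed) cannot count as responders, power at 30% is 0.88 / 0.85 / 0.82.

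**The case against.** The strongest reply is that the opening criterion is itself a futility screen. A 10% dose that can open only by a clinical response fails to reach the nine extra patients with probability 0.92, 0.79 or 0.65, above 0.51, and conditional power at 30% exceeds the stated 90%. That stands. A reader might infer that the true type I error is 17 to 21%; the documents do not support this, because those figures condition on opening and the per-dose-level probability stays below 10%. The 0.51, however, is stated for a cohort that has been opened, so the comparison with 0.21 to 0.26 is like with like.

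A reader might also infer that at least one of the two assumed expansions must open on a BCAD, since "The MTD is defined as the highest dose level of VK-2019 at which fewer than two DLTs are observed" and so is a single level. That is not established. Section 6.1.1 allows a dose to be chosen for expansion on exposure grounds, two expanded levels is a sizing assumption, and the note to Figure 1 says the number of expansions depends on observed activity. A BCAD can also be biological, with no RECIST response needed.

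Nor is the triggering patient always among the 16. Sections 6.2.4 and 6.2.5 allow intra-patient escalation, so a patient moved up into a dose might trigger its BCAD without having been enrolled there.

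Finally, no confirmatory inference is planned (Section 14), the go decision is discretionary, and the SAP, written for an abbreviated report, plans no interim output (7.15). This limits the consequence to how the futility check and the pooled response rate are read. It does not make the 0.51 right for this route.

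**Conclusion.** The 10% / 90% / 0.51 are correct for a first 16 not selected on response, and only for that. For an expansion opened solely by the response of an escalation patient enrolled at that dose and counted in the 16, early stopping at a true 10% is about half what is printed when every response counts.

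The result does not extend to expansions opened as the MTD, by biological BCAD or on exposure grounds, or to a triggering patient outside the 16. How often the sole-clinical route would occur is unknown.

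Under every response definition checked, early stopping is below the matching unselected value. It need not be below 0.51: with confirmed-only counting and an any-response rate of 10%, it is 0.51 at a 70% confirmation share and 0.60 at 60%. The point should be addressed, but it does not invalidate the design.

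**What to change.** 1. First choose one response definition for stage 1 and for the 5/25 test. Reconcile Phase 2a Dose Expansion (Section 4), Initiation of Phase 2a Expansion Cohorts and SAP 2.1.3 with the unconditional continuation in Sample Size Determination and with Interim Analysis. The direct clash is with the former, since Interim Analysis says only when accrual stops.
2. In Sample Size Determination, the synopsis and SAP Section 5, state that 10% / 90% / 0.51 assume an unselected, response-evaluable first 16. Add the figures for a cohort opened solely by a clinical BCAD response under the chosen definition: early stop 0.21 to 0.26 and reaching 5/25 0.17 to 0.21 if every response counts. Label them as conditional on opening, and show them beside the per-dose-level figures (0.02 to 0.08) and conditional power (0.93 to 0.96).
3. Record which criterion opened each expansion, and report the response rate in patients enrolled after the decision beside the pooled rate.
4. Keep the caps of 16 and 25, and restate the operating characteristics for the number of response-evaluable patients actually among them.

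The cost is some less favourable printed figures, one recorded item per expansion and one imprecise extra line: with ten patients after the decision, 1/10 has an exact 95% interval of 0.3% to 44.5%. No patients are added.
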